## VII. SCHEDULE OF EVENTS

PROCEDURE	Baseline (Pre-treatment)	Week 0 Clinic Visit	Week 2 Phone Visit	Week 4 Clinic Visit	Week 6 Phone Visit	Week 8 Clinic Visit	Week 10 Phone Visit	Week 12 Clinic Visit	Week 14 Phone Visit	 Week 16 Clinic Visit (  End of Study) (  Placebo Crossover)	 Month 6 Clinic Visit	 Month 9 Clinic Visit	 Month 12 Clinic Visit (End of Study)
Signed, written informed consent	X												
Medical history	X												
Physical examination	X									X	X	X	X
Blood pressure, pulse, O 2 saturation	X									X			
Penile injection: Caverject 20mcg/cc	X									X			
Penile curvature assessment & photos	X									X			
Penile ultrasound	X									X			
IIEF questionnaire	X									X			
Randomization	X												
Penile injection: BTX-A or  Placebo		X		X		X		X					
Collect AE information		X	X	X	X	X	X	X	X	X	X	X	X
Concomitant meds	X	X		X		X		X		X	X	X	X

End of study for subjects receiving BOTOX and did not develop ED (as defined as a drop in IIEF scores of more than 4 points from Baseline IIEF score).

End of study participation for subjects receiving placebo and develop ED.

For subjects receiving placebo, crossover to BOTOX treatment will begin by repeating the study schedule as for Week 0 to Week 16.

Continuation visits for subjects receiving BOTOX and developed ED.

## VIII. PROCEDURES

Subjects who meet the inclusion criteria for the study will be randomized to either the treatment or placebo arm. Prior to treatment, all subjects will have a penile injection with Caverject 20mcg/cc to induce a penile erection. During the erect state, penile curvature will be assessed, pictures will be taken for later measurement of penile curvature, and ultrasound will be used to assess penile blood flow and plaque size. A penile duplex with intercavernosal injections of a vasoactive substance is part of our standard care for Peyronies disease diagnosis. Subjects will also be asked to complete the International Index of Erectile Function (IIEF) questionnaire.

Injections will be performed using our standard protocol currently used for verapamil injections, but instead we will be using 100 units of BTX-A in 10cc of preservative free normal saline, or 10cc of preservative free normal saline for placebo and plaque breakdown injections. The standard injection procedure consists of the following:

1. Subjects will be explained the risks and benefits of the procedure and will give informed consent.
2. Blood pressure, pulse, and oxygen saturation will be monitored throughout the procedure.
3. A penile block with 10cc of lidocaine without epinephrine will be given, followed by an observation period of 10 minutes to assure no immediate adverse reaction to lidocaine.
4. Approximately 20 to 30 injections with a 20 gage needle will be given directly into the penile plaque. The skin will not be punctured with each injection, but the needle will move within the plaque. Injection solution will consist of 100 units of BTX-A in 10 cc of preservative free normal saline, or 10 cc of preservative free normal saline.
5. Subjects in the placebo arm will only receive 10 cc of preservative free normal saline.
6. Subjects will be monitored for 1 hour after the procedure to ensure that their vital signs are stable and that there are no signs of penile hematoma.
7. Safety will be assessed by following the subject closely for one hour after the procedure.
8. Subjects will be given strict instructions to call and return to the clinic or the ER for any adverse side effects.

Subjects randomized to ARM 1 will receive one injection of 10 cc preservative normal saline at study start (week 0), followed by 100 U Botox in 10cc saline at visit two (week 4), then saline injections at weeks 8 and 12, thus a total of 4 injections (1 saline, 1 Botox, 2 saline).

Subjects randomized to ARM 2 will receive one injection of 10cc preservative normal saline at Weeks 0, 4, 8 and 12.

All subjects will be telephoned two weeks after each injection to inquire on the occurrence of any adverse events. Subjects will be asked a general, non-direct question such as, "How have you been feeling since the last visit?" Direct questioning will then be done as appropriate.

At the completion of 16 weeks (4 weeks after last treatment), subjects will have a repeat penile injection of Caverject, penile pictures will be taken, and penile ultrasonography will be performed. Subjects will also be asked to complete the IIEF again.

The Week 16 Visit will be the end of the study participation for those subjects in Arm 1 and who did not develop ED (as defined as a drop in IIEF scores of more than 4 points from Baseline IIEF score). Subjects developing ED, will have continuation visits at Months 6, 9, and 12. At these visits, a complete physical will be done. Information about any adverse events and changes in concomitant medications will be collected. The subjects will complete the IIEF questionnaire.

If at the end of 16 weeks there is a significant improvement in the subjects treated with BTX-A as compared to the placebo arm, the men in the placebo arm will be given the option to cross over into the treatment arm and complete a 12 week course of BTX-A injections (1 saline injection, 1 Botox injection, 2 saline injections). For those in Arm 2 who develop ED, participation will end after the Week 16 visit.

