## VI. RANDOMIZATION PROCEDURES:

The subjects will be randomized to the arms as they are enrolled and meet eligibility criteria. The odd number (1, 3, 5...) of subjects will be in ARM 1 and even numbers (2, 4, 6...) of subjects will be in the ARM 2. The randomization scheme will not result in selection bias.

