#### **C. Data Collection:**

Data will be collected using the protocol's case report forms. Participants will be identified on the forms by their study ID number. The clinical study coordinator of the trial will maintain the codes that link the name of the participant to their study ID number. The study coordinator will maintain the code in a secured cabinet and the code will be kept confidential. Only the clinical study coordinator and PI can access and view the codes. Data quality will be monitored by random inspection of the completed forms by a member of the Scott Department of Urology's Research

Administration QA unit. Any problems detected by QA personnel will be discussed with the PI.

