## **XVIII. CONFIDENTIALITY**

Each subject will be assigned a unique, consecutive three-digit identification number (i.e., 001, 002, ...). The study number will be utilized for identification of the subject throughout the study. The clinical study coordinator of the trial will maintain the code that links the name of the participant to their study ID number. The study coordinator will maintain the code in a secured cabinet and the code will be kept confidential. Only the clinical study coordinator and PI can access and view the codes.

The research records will be maintained in the Scott Department of Urology. The computers used for this study are password protected. The data will be kept by the clinical coordinator in a secure locked area. Areas are protected after hours by an electronic door locking systems. The Scott Department of Urology adheres to the HIPAA guidelines.

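### Direct adverse event questions are left to staff discretion in a trial with alternating allocation and no stated masking, so the descriptive safety record may be collected unequally between arms

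*Combined protocol and SAP*

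**What the plan says.** Section VIII (Procedures) sets the calls for both arms alike: "All subjects will be telephoned two weeks after each injection to inquire on the occurrence of any adverse events". The Schedule of Events places them at Weeks 2, 6, 10 and 14. Each call opens with a general question, for which one example is given. The next sentence reads: "Direct questioning will then be done as appropriate". Neither that section nor the safety sections (XIII and XIV) supplies a list of events to ask about, a script, or a rule for when direct questions are due.

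Allocation is by alternation (section VI): "The odd number (1, 3, 5...) of subjects will be in ARM 1 and even numbers (2, 4, 6...) of subjects" in Arm 2. Section XVIII adds "Each subject will be assigned a unique, consecutive three-digit identification number", and section XIII.C says "Participants will be identified on the forms by their study ID number". The study coordinator and the PI alone can see the code linking names to numbers. Section XIII.D has the investigators, the coordinator, or both document adverse events. Section V calls the trial randomized and placebo-controlled; no section says that subjects, callers or event recorders are masked.

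As section VIII describes the treatments, both arms receive saline at Week 0 and Arm 1 receives its single BTX-A injection at Week 4.

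**The concern.** Reports of adverse events depend on how they are sought. An open question followed by optional direct questions gives fewer reports from a man who is not pressed than from one who is. If the person asking has an idea of the arm, the pressing can differ by arm without anyone intending it. It could go either way: closer questioning of Arm 1 creates an apparent excess, and lighter questioning hides a real one.

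Section IX names weakness spreading to nearby muscles, swallowing difficulty and breathing difficulty among the BOTOX risks, and calls the risk of erectile dysfunction unknown. A pilot is where a first, even-handed description of these events should come from. With so few men, one or two reports more or fewer would change how that description reads.

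**Working it through.** **Can staff infer the arm?** Applying the odd/even rule to enrolled subjects 1 to 20 gives 10 men in Arm 1 and 10 in Arm 2, matching section XI. Anyone who knows a man's place in the enrolment order therefore knows his arm. The coordinator and the PI hold the identity code, and section XIII.D lets the coordinator or the investigators document events. The documents do not say who makes the calls.

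**Which events have no other structured measure?**

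- Erectile function: within the 16 weeks, the IIEF is completed at Baseline and Week 16. Its items on erections look back four weeks (Appendix I), so the second form covers 16 − 4 = Week 12 to Week 16. An erection problem that begins after the Week 4 injection and resolves by about Week 12 can be recorded only through adverse event questioning.
- Weakness, swallowing and breathing: no questionnaire or scheduled test targets these after any injection.
- Timing: apart from the one-hour observation after injection, the Week 6 call is the first scheduled contact after BTX-A.

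**How large could the distortion be?** The plan gives no adverse event rates, so every rate here is an assumption. Let *p* be the true risk, equal in both arms, and *s*₁ and *s*₂ the proportions of events brought out by questioning in Arms 1 and 2. With 10 men per arm:

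- expected men with a reported event = 10 × *p* × *s*
- false excess in Arm 1 = 10 × *p* × (*s*₁ − *s*₂)
- ratio of reported risks = *s*₁ / *s*₂, in which *p* cancels

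| True risk | Expected reports, 90% vs 50% detected | False excess | P(Arm 1 shows more), 90% vs 50% | P(Arm 1 shows more), 70% in both |
|---|---|---|---|---|
| 10% | 0.9 vs 0.5 | 0.4 | 44% | 31% |
| 20% | 1.8 vs 1.0 | 0.8 | 57% | 37% |
| 30% | 2.7 vs 1.5 | 1.2 | 65% | 39% |
| 50% | 4.5 vs 2.5 | 2.0 | 77% | 41% |

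The probabilities are exact, from two independent binomials of size 10. With equal detection, Arm 2 is as likely to show more reports as Arm 1. At a milder 90% versus 70%, the false excess runs from 10 × 0.10 × 0.20 = 0.2 to 10 × 0.50 × 0.20 = 1.0 men.

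Two further cases at an assumed true risk of 40%: detection of 90% versus 60% gives 3.6 versus 2.4 men (ratio 0.90/0.60 = 1.5), and 80% versus 70% gives 3.2 versus 2.8 men (ratio 0.80/0.70 = 1.14). These ratios only restate the assumed detection rates. The excess is proportional to *p*, so for events that section IX calls rare the expected number of spurious reports is close to zero.

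**The case against.** The strongest reply is that the direct questions are simply follow-up of whatever a man mentions, that call times and opening question are the same in both arms, and that the root cause is alternation without masking. Concealed allocation and a masked caller would remove the mechanism that makes probing differ by arm, whereas a fixed list leaves a caller who knows the arm free to interpret a vague answer. Much of this stands. Follow-up is a fair reading of the sentence, but the text does not limit direct questions to it, and even follow-up can be pursued more or less hard. Masking would not cure under-reporting to an open question or variation between callers.

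Four stronger readings are tempting, and the documents do not support them.

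- *The arm can be read from the subject number.* This holds only if identification numbers follow enrolment order. Section XVIII does not say when they are issued, and section XI plans to screen 45 men for 20 places. Numbers issued at screening need not match the arm by parity, although enrolment order would still reveal it.
- *A planned safety comparison is biased.* Section XII lists curvature, blood flow, plaque size and IIEF scores. Adverse events are not an outcome there and no test of them is specified.
- *Erection problems go unmeasured unless a caller probes.* The IIEF is a fixed form in both arms, and the protocol defines ED by a fall in its score. The gap is limited to transient problems before about Week 12.
- *The calls are the only route.* Events are also collected at clinic visits, and men are told to call or return if they have adverse effects. These routes help, but none uses a fixed list.

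**Conclusion.** The concern holds in limited form. Discretionary direct questions, predictable allocation and the absence of stated masking together allow unequal ascertainment; they do not show that it occurred. What is at risk is the descriptive safety record for weakness, swallowing or breathing problems, and for transient erection problems between Week 4 and about Week 12. The curvature endpoint and the Week 16 IIEF are not affected by this route.

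The size is unknown. With 10 men per arm it would plausibly be about one or two men, on the assumption that true risk is equal and detection differs substantially between arms; with milder differences or rare events it is less than one. It is a minor point, worth acting on because the remedy is cheap.

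**What to change.** Keep the open question first and record what the man volunteers. Then ask every man in both arms the same short scripted list, in the same words, with a yes/no answer recorded for each item. Do this at the Week 2, 6, 10 and 14 calls and at each clinic visit. Draw the items from section IX: weakness, difficulty swallowing, difficulty breathing, rash or itching, pain or bruising at the injection site, and any change in erections. Report spontaneous and solicited events separately by arm. Because both arms have had only saline by Week 2, a marked difference between arms in solicited events at that call would be a warning sign about the questioning, though a weak one with 10 men per arm.

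The cost is a one-page form and roughly two minutes per contact, using existing contacts and staff. The downside is that more minor background events will be recorded in both arms, which is why the two sources should be tabulated apart. No dose, schedule or clinical rule changes. The list reduces the effect of staff knowing the arm but does not replace concealed random allocation, identifiers that do not reveal the arm, and masked callers and event recorders.

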## **IX. RISKS**

**BOTOX®:** It is expected that some participants may have some or all of the following side effects when given BOTOX®. Other side effects may occur which were not seen before. Side effects are usually temporary and manageable. However, it is possible they could cause serious disease or death. The study may include risks that are unknown at this time.

There have been rare reports of serious and/or immediate or even deadly abnormally sensitive reactions after treatment with BOTOX. These reactions include allergic reaction, skin rash, itching, swelling, and difficulty in breathing.

There have been rare reports of sudden death, sometimes associated with difficulty in swallowing or pneumonia. There have also been rare reports of heart problems (including irregular heart beats and heart attack, some resulting in death). Some of these patients were already at risk for heart disease. It is not known if BOTOX actually caused these problems.

It should not be used when infection is present at the injection site or in people known to be abnormally sensitive to BOTOX.

The following events have been observed since it has been marketed: skin rash, itching, and allergic reaction. In general, these side effects occur within the first week following injection and, while usually temporary, they may last several months. Pain, tenderness, or bruising around the injection site may also occur. Local weakness of the injected muscle(s) is expected. Weakness of nearby muscles may also occur due to spread of BOTOX.

BOTOX contains albumin, which comes from human blood. Although the blood is rigorously tested, there is an extremely remote risk for the transmission of viruses and similar infectious agents.

CAVERJECT®: Possible side effects of therapy with Caverject are penile pain after injection, usually mild to moderate in severity. A potentially serious reaction is priapism; therefore, patients should be instructed to seek medical attention if an erection last for more than 4 hours.

The injection can induce a small amount of bleeding at the site and a hematoma may form. There may be an occurrence of nodules or hard tissue in the penis, redness, and swelling.

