Hypertension was reported in about 2% of patients. Headaches and dizziness were reported in 2% or less of patients. About 1% of the patients complained of backache. Upper respiratory infections were reported in 4% and flu-like symptoms in 2%. Sinusitis was reported in 2% and nasal congestion and coughs in 1%. Prostatic disorders were reported in 2%. Localized pain at injection site was reported in about 2% and trauma, such as, injuries, fractures, abrasions, lacerations, and dislocations were reported in 2%.

Less than 1% of patients in clinical studies reported the following events that were judged as possibly related to the use of Caverject: testicular pain and disorder, scrotal disorder, scrotal edema, hematuria, impaired urination, urinary frequency, urinary urgency, pelvic pain, hypotension, vasodilation, peripheral vascular disorder, supraventricular extrasystoles, vasovagal reaction, hypesthesia, non-generalized weakness, diaphoresis, rash, non-application site pruritus, skin neoplasm, nausea, dry mouth, increased serum creatinine, leg cramps, and mydriasis.

LIDOCAINE®: Adverse experiences with Lidocaine are, in general, dose-related and may result form high plasma levels caused by excessive dosage, rapid absorption or inadvertent intravascular injection, or may result from a hypersensitivity, idiosyncrasy or diminished tolerance on the part of the patient.

Central nervous system symptoms that may be experienced are lightheadedness, nervenousness, apprehension, euphoria, confusion, dizziness, drowsiness, tinnitus, blurred or double vision, vomiting, sensations of heat, cold or numbness, twitching, tremors, convulsions, unconsciousness, respiratory depression and arrest.

Cardiovascular manifestations are usually depressant and are characterized by bradycardia, hypotension, and cardiovascular collapse, which may lead to cardiac arrest.

Allergic reactions are characterized by cutaneous lesions, urticaria, edema, or anaphylactoid reactions. These reactions to Lidocaine are extremely rare.

The effect of the study treatments on the ability to have erections and to have intercourse is unknown. It is not known whether the treatments the subject receives in this study will worsen or will improve his ability to have intercourse

Additional risks that may be experience by subjects participating in this study are:

The risk of developing erectile dysfunction after these injections is unknown.

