## **XII. DATA ANALYSIS**

- A. The primary outcome measure will be:
  - 1. change in penile curvature, as measured by a protractor from pictures taken at baseline versus the end of treatment at 16 weeks
- B. Secondary outcomes will be measured objectively and subjectively.
- C. Objective measures will be:
  - 1. improvements in penile blood flow
  - 2. reduction in penile plaque size as seen on ultrasound
- D. Subjective measures will be:

1. changes in IIEF scores

As mentioned above, these objective and subjective measurements will be performed before and after the 16 week treatment.

Data will be analyzed using a t-test to compare differences between the two groups.

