**Please circle your answer**

1. Over the past 4 weeks, how often were you able to get an erection during sexual activity?

No sexual activity .....	0
Almost never/never .....	1
A few times (much less than half of the time).....	2
Sometimes (about half of the time) .....	3
Most times (much more than half of the time).....	4
Almost always/always .....	5
  
2. Over the past 4 weeks when you had erections with sexual stimulation, how often were your erections hard enough for penetration?

No sexual activity .....	0
Almost never/never .....	1
A few times (much less than half of the time).....	2
Sometimes (about half of the time) .....	3
Most times (much more than half of the time).....	4
Almost always/always .....	5
  
3. Over the past 4 weeks when you attempted sexual intercourse, how often were you able to penetrate (enter) your partner?

Did not attempt intercourse .....	0
Almost never/never .....	1
A few times (much less than half of the time).....	2
Sometimes (about half of the time) .....	3
Most times (much more than half of the time).....	4
Almost always/always .....	5
  
4. Over the past 4 weeks during intercourse, how often were you able to maintain your erection after you had penetrated (entered) your partner?

Did not attempt intercourse .....	0
Almost never/never .....	1
A few times (much less than half of the time).....	2
Sometimes (about half of the time) .....	3
Most times (much more than half of the time).....	4
Almost always/always .....	5
  
5. Over the past four weeks, during sexual intercourse, how difficult was it to maintain your erection to completion of intercourse?

Did not attempt intercourse .....	0
Extremely difficult .....	1
Very difficult .....	2
Difficult .....	3
Slightly difficult .....	4
Not difficult .....	5
  
6. Over the past four weeks, how many times have you attempted sexual intercourse?

No attempts.....	0
One to two attempts .....	1
Three to four attempts.....	2
Five to six attempts .....	3
Seven to ten attempts .....	4
Eleven or more attempts .....	5
  
7. Over the past four weeks when you attempted sexual intercourse, how often was it satisfactory for you?

Did not attempt intercourse .....	0
Almost never/never .....	1
A few times (much less than half of the time).....	2
Sometimes (about half of the time) .....	3
Most times (much more than half of the time).....	4
Almost always/always .....	5

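### In the 16 weeks the IIEF is scored only at Baseline and Week 16, so erectile dysfunction that resolves within 8 weeks of the single Week 4 BOTOX injection cannot meet the plan's ED definition

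*Combined protocol and SAP*

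**What the plan says.** Section VIII (Procedures) has Arm 1 receive saline at Week 0, "followed by 100 U Botox in 10cc saline at visit two (week 4), then saline injections at weeks 8 and 12". Arm 2 receives saline at all four visits.

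The outcome visit is placed as follows: "At the completion of 16 weeks (4 weeks after last treatment), subjects will have a repeat penile injection of Caverject". Of the questionnaire at that visit the section says: "Subjects will also be asked to complete the IIEF again". The Section VII table agrees, marking the IIEF at Baseline and Week 16 and at no visit between. Section XII agrees too: "these objective and subjective measurements will be performed before and after the 16 week treatment".

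The questionnaire in Appendix I begins "Over the past 4 weeks, how often were you able to get an erection during sexual activity", and all 15 items use the same four-week look-back.

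Sections V, VII and VIII define ED in one way only, as an IIEF fall of over 4 points from Baseline. In Arm 1 that status decides who returns at Months 6, 9 and 12. In Arm 2 it ends participation at Week 16. Section IX states: "The risk of developing erectile dysfunction after these injections is unknown".

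**The concern.** A questionnaire with a four-week look-back, given once, sees four weeks. Here those are the last four of the twelve that follow the toxin. A man whose erectile function falls after Week 4 and is back to his Baseline level by Week 12 is classified as not having developed ED, however deep the fall was.

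Two results are affected. The number of men with ED by the plan's definition becomes a count of those with ED in Weeks 12 to 16, and a reader may take it as the count over the whole post-treatment period. The secondary comparison of IIEF change leaves out the same eight weeks. With 10 men per arm, one man classified differently moves an arm's ED proportion by 1/10, or 10 percentage points. Men who cross over repeat the Week 0 to Week 16 schedule, so the gap recurs in them.

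**Working it through.** **Inputs.** Injections at Weeks 0, 4, 8 and 12, with BOTOX at Week 4 only (Section VIII). IIEF at Baseline and Week 16 (Sections VII, VIII and XII). Look-back of 4 weeks (Appendix I).

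**The plan's own interval.** Last injection to outcome visit: 16 − 12 = 4 weeks. This matches Section VIII. That last injection is saline; from BOTOX the interval is 16 − 4 = 12 weeks.

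**Window seen by the Week 16 form.** In study time: (16 − 4) to 16 = Weeks 12 to 16. In time since BOTOX: (12 − 4) to (16 − 4) = weeks 8 to 12. Covered: 4/12 = 33%. Not covered: 8/12 = 67%, which is study Weeks 4 to 12.

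**Which episodes the form can see.** An episode starting s weeks after BOTOX and lasting d weeks overlaps the window by max(0, min(12, s + d) − max(8, s)) weeks.

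| Duration d (weeks) | Overlap if s = 0 | Overlap if s = 1 |
|---|---|---|
| 2, 4 or 6 | 0 | 0 |
| 8 | 0 | 1 |
| 10 | 2 | 3 |
| 12 | 4 | 4 |

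The durations are illustrative; the documents give none. A partial overlap need not produce a fall of over 4 points.

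**Coverage if forms are added at existing clinic visits.**

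| IIEF visits after Baseline | Post-BOTOX weeks covered |
|---|---|
| Week 16 | 4 of 12 |
| Weeks 12 and 16 | 8 of 12 |
| Weeks 8, 12 and 16 | 12 of 12, no gap |

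**Dependence on the injection schedule.** The window in time since BOTOX rests on the single Week 4 injection in Section VIII. The Section VII injection row, which names BTX-A or placebo at all four visits, and the Arm 1 description in Section V do not show this. Counted from an injection at Week 0, 8 or 12, the Week 16 form would cover weeks 12 to 16, 4 to 8, or 0 to 4 afterwards. On any reading, study Weeks 0 to 12 have no IIEF coverage.

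**The case against.** The strongest reply is that ED would not go unseen. Adverse events are collected at every visit and call. Four of those contacts (Weeks 6, 8, 10 and 12) fall 2, 4, 6 and 8 weeks after BOTOX. Direct questions may follow the opening one on the calls, men are told to report adverse effects, and events are followed until resolved. This stands, and it limits the point: a reader might infer that transient ED would go wholly unrecorded, and the documents do not support that. What remains is that the calls open with a general question, no question on erectile function is specified, and an adverse event report yields no IIEF score and does not enter the ED rule.

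A second tempting inference is that the measured window is the one furthest from the expected onset. Section IX does say "In general, these side effects occur within the first week following injection and, while usually temporary, they may last several months", but that sentence follows directly on skin rash, itching and allergic reaction, and it allows for effects lasting months. Section III describes denervation as slowly reversing, which could carry an effect into weeks 8 to 12. The documents give no onset or duration for ED, so the sentence is not evidence in either direction.

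Third, a man who has recovered by Week 16 has no continuing ED to follow, so his leaving then is not clearly a failure of the continuation rule. A before-and-after secondary endpoint is also a legitimate choice in a 20-man pilot. Both points stand. They do not answer the gap in describing an effect whose risk the protocol calls unknown.

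Finally, more forms give more chances for a spurious fall. Items 1 to 10 each offer a score of 0 for no activity, no attempt or no intercourse, so abstinence after needling can lower the score without ED. An any-visit count has three chances for this instead of one. This stands and shapes the reporting below.

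**Conclusion.** The point holds in a limited form. Taking the single Week 4 injection as Section VIII describes it, the IIEF leaves 8 of the 12 post-BOTOX weeks unscored. ED that has resolved by Week 12 cannot meet the plan's only ED definition and does not enter the secondary IIEF comparison. That follows from the schedule and the look-back, and needs no assumption about how common or how early ED is.

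The documents do not show that such episodes are likely, or that they would escape adverse event recording. The primary curvature outcome is unaffected. The change is worth making because the gap concerns a risk stated to be unknown and can be closed at visits already planned.

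**What to change.** In the Section VII table and in Section VIII, add the IIEF at the Week 8 and Week 12 clinic visits in both arms, completed before that visit's injection. The forms then describe Weeks 4 to 8, 8 to 12 and 12 to 16.

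Keep Week 16 as the secondary-outcome time point and as the basis of the existing ED rule. In Section XII, add a descriptive report by arm of the number of men with a fall of over 4 points at each of Weeks 8, 12 and 16 and at any of them. Show alongside it how many of those men gave scores of 0 for no activity or no attempt. The placebo arm has the same needling and the same three looks, so it serves as the control for both effects.

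The sponsor should state, for each arm, whether a fall at Week 8 or 12 has any bearing on continuation visits or crossover. The Section VII injection row and the Section V description of Arm 1 must be reconciled with the Section VIII schedule.

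Cost: a protocol amendment and two extra self-completed 15-item forms per man, with no new visit, procedure or staff. Completion time is not in the documents; that it is short is an assumption. The any-visit count will be higher in both arms because of transient or abstinence-related falls, and should be read only as a comparison between arms.
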